4.1.4.2 Methotrexate treatment

Treatment will start on Visit 2 (Day 1). Patients randomised to the methotrexate arm will be administered intravenous bolus injections once a week. See methotrexate SPC/PI for warnings and precautions before initiating methotrexate treatment.

Patients will start on 40 mg/m^2 methotrexate and continue (see [Table 4.1.4.2: 1](#)) on this dose in the absence of AEs necessitating dose reduction (see [Table 4.1.4.2: 2](#)). If no evidence of drug-related AEs, the methotrexate dose may be escalated to 50 mg/m^2 after two weeks of treatment at the discretion of the investigator.

In case the dose has been reduced once, it should not be escalated again.

Dose continuation and escalation, methotrexate

Table 4.1.4.2: 1 Methotrexate dose continuation and escalation criteria

| Parameter | Recommended dose | After at least two consecutive weeks (only if current dose is 40 mg/m^2) ¹ |
|--|-----------------------|--|
| Neutrophil count $\geq 1.5 \times 10^9/\text{l}$, and Platelet count $\geq 75 \times 10^9/\text{l}$, and Calculated creatinine clearance ² $\geq 50 \text{ ml/min}$, and Mucositis CTCAE grade ≤ 1 , and Other drug-related AE CTCAE grade ≤ 1 | Continue current dose | Escalate to 50 mg/m^2 |
| | | |

1 At the discretion of the investigator

2 Calculated according to Cockcroft-Gault formula, see [Appendix 2](#).

Dose reduction, methotrexate

Dose reductions will apply to individual patients only, as described in Table 4.1.4.2: 2. Once the dose has been reduced, it may not be increased later.

Proprietary confidential information. © 2019 Boehringer Ingelheim International GmbH or one or more of its affiliated companies

Table 4.1.4.2: 2 Methotrexate dose reduction scheme

| Event |
|---|
| Any of the following: 
• Neutrophil count $<1.5 \times 10^9/l$• Platelet count $<75 \times 10^9/l$• Mucositis CTCAE grade > 1• Calculated creatinine clearance $<50 \text{ ml/min}$• Any drug-related CTCAE grade ≥ 2 |
| Action |
| Interrupt methotrexate treatment until patient has recovered or reaches the baseline ¹ values. Discontinue study medication if: 
• Drug-related AEs requiring a treatment pause of more than three consecutive weeks• Any CTCAE grade ≥ 2 when treated with a dose of 20 mg/m^2 per week. |
| Dose reduction scheme |
| Resume treatment at reduced dose according to: 
• 40 mg/m^2 if the dose prior to the interruption was 50 mg/m^2• 30 mg/m^2 if the dose prior to the interruption was 40 mg/m^2• 20 mg/m^2 if the dose prior to the interruption was 30 mg/m^2 No dose reduction is allowed below 20 mg/m^2 . |

1 Baseline is defined as the CTCAE grade prior to start of treatment

In the event of a treatment pause, subsequent visits should not be delayed.

In the event of any unrelated AE, the investigator may choose to skip one administration to allow the patient to recover, but no dose reduction should occur. If the investigator chooses to interrupt the study medication longer than 3 consecutive weeks but believes that the patient would derive clinical benefit from continuing medication, the decision to continue will be made by the sponsor in agreement with the investigator.

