3.3.4 Removal of patients from this trial or assessments

3.3.4.1 Removal of individual patients

A patient is to be permanently discontinued from study medication if:

1. The patient withdraws consent to further study medication.
2. Radiologically documented progressive disease (refer to [Section 5.1.2](#)).
3. Pregnancy (refer to [Section 5.2.2.2.1](#)).
4. Diagnosis of ILD.
5. Need further dose reductions but not allowed according to the protocol (see [Section 4.1.4](#)).

Proprietary confidential information. © 2019 Boehringer Ingelheim International GmbH or one or more of its affiliated companies

6. The patient is no longer able to receive the study medication (e.g. adverse events, concomitant diagnoses, concomitant therapies interfering with Afatinib or methotrexate, or administrative reasons), significant deviation from the protocol.

At the time of study medication withdrawal the patient should return for a complete EOT visit. The information, including the reason for treatment discontinuation, will be recorded in the electronic Case Report Form (eCRF). See also [Section 6.2.3](#) and the [Flow Chart](#).

For safety reasons, the patient should come to the FUV four weeks after the EOT visit. Following the FUV, the patient will continue in the observational period. During this period vital status information, anti-cancer therapy, and related SAEs and AESIs will be collected every four weeks. For patients who progressed on treatment, the observation period for overall survival starts after the FUV (end of residual effect) visit. For patients who have not progressed on treatment, this period starts after the last additional FU visit. The observational period ends when the patient deceases.

A patient should be withdrawn from trial if:

1. The patient withdraws consent for any further trial procedures and follow-up activities.

Data of a withdrawn patients, regardless the patient received study medication or not, and the reason of withdrawal must be recorded in the eCRF.

Unless a randomised patient withdraws consent to be followed up, vital status information will be collected (e.g. by phone contact or check of medical records) until the entire trial has ended.

Patients who withdraw from the trial after randomization will not be replaced.

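### For mucositis judged unrelated to methotrexate, the dose-reduction table and the sentence under it give opposite doses; separately, the stopping bullet at 20 mg/m² lacks a drug-related limit

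*Protocol*

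**What the plan says.** All of this stands in Protocol Section 4.1.4.2 unless another place is named.

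- **Event row of Table 4.1.4.2: 2.** Five triggers lead to interruption and then to a lower dose: neutrophil, platelet and creatinine clearance limits, "Mucositis CTCAE grade > 1", and a catch-all beginning "Any drug-related CTCAE grade" (grade 2 or higher). Only the catch-all mentions relatedness.
- **Permanence.** "Once the dose has been reduced, it may not be increased later".
- **Stopping bullets, Action row.** The first is "Drug-related AEs requiring a treatment pause of more than three consecutive weeks". The second is "Any CTCAE grade ≥ 2 when treated with a dose of" 20 mg/m² per week.
- **Sentence under the table.** Its rule reads: "any unrelated AE, the investigator may choose to skip one administration to allow the patient to recover, but no dose reduction should occur".
- **Table 4.1.4.2: 1.** Continuing the current dose and escalating both require mucositis of grade 1 or lower, with no attribution, and then "Other drug-related AE CTCAE grade" 1 or lower.
- **Section 3.3.4.1, criterion 5.** Treatment stops on "Need further dose reductions but not allowed according to the protocol".

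The synopsis, Section 3.1 and Section 4.1.3 describe methotrexate reduction as a response to drug-related AEs. In the afatinib arm, Table 4.1.4.1: 1 is headed as covering events related to study medication. The text after it rules out reduction for AEs other than those the table lists.

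**The concern.** These are working dosing rules for the comparator. A site that follows the table lowers methotrexate for an event it judges the drug did not cause; a site that follows the sentence under the table does not. The reduction cannot be reversed. At the lowest dose, the literal wording of the second stopping bullet ends treatment for an unrelated grade 2 event of any kind.

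The ambiguity also reaches the analysis records. SAP Table 6.2: 1, code C1, counts failure to pause and reduce according to the protocol as an important violation. C1 is not among the codes marked for identification by program, so someone must decide which of the two rules was the protocol.

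**Working it through.** No sample size, power or event count is involved. The check sets the rules side by side.

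**1. New or worsened grade 2 mucositis, judged unrelated.** Dose levels are those of the reduction scheme in Table 4.1.4.2: 2.

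| Current dose (mg/m²) | Table | Cut under the table | Sentence under the table |
|---|---|---|---|
| 50 | resume at 40 | (50 − 40)/50 = 20% | stay at 50, 0% |
| 40 | resume at 30 | (40 − 30)/40 = 25% | stay at 40, 0% |
| 30 | resume at 20 | (30 − 20)/30 = 33% | stay at 30, 0% |

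The sentence lets the investigator skip one dose but excludes a reduction, so both rules cannot be followed. Unchanged baseline mucositis is left out, because Section 5.2.2.1.1 defines an AE to include an exacerbation of a pre-existing condition.

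**2. Laboratory triggers.** The neutrophil, platelet and creatinine clearance limits also lack attribution, so 1 of 5 triggers says drug-related. Under Section 5.2.2.1.6 a laboratory change is an AE if judged clinically relevant. Where such a value is recorded as an AE and judged unrelated, the same conflict arises.

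**3. Stopping bullet.** One of the 2 stopping bullets says drug-related. Take an unrelated grade 2 AE that is not one of the listed events:

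- At 30, 40 or 50 mg/m² no trigger is met. The dose stays, and one administration may be skipped.
- At 20 mg/m² the bullet, read literally, gives a permanent stop.
- Criterion 5 is not met, because an unrelated, unlisted AE calls for no reduction. The literal bullet is therefore broader than criterion 5.
- The sentence under the table has no dose-level limit, but it forbids reduction and says nothing about stopping. This is tension, not contradiction.

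**4. Adding 'drug-related' to the mucositis line of Table 4.1.4.2: 2 alone.** Table 4.1.4.2: 1 would still require grade 1 or lower, whatever the cause, to continue the current dose. A patient with unrelated grade 2 mucositis would fail that condition, while the second table and the sentence would call for no reduction. The conflict would only move.

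**5. Exempting the listed events in the sentence instead.** Table 4.1.4.2: 1 says do not continue at the current dose, Table 4.1.4.2: 2 says reduce, and the sentence no longer applies. The three agree.

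**The case against.** The strongest reply is that ignoring cause is deliberate. Both methotrexate tables list the same four parameters without attribution, followed by a drug-related catch-all. Sections 2.3 and 4.2.3 name stomatitis among methotrexate's most common side effects. A rule that let a site attribute grade 2 mucositis to something else and carry on at full dose could be unsafe. On this reading the table is the specific rule and the sentence covers everything else. That may well be the intent, and it decides which edit is preferable. It does not remove the conflict: the sentence says any unrelated AE and, unlike the afatinib text, does not except listed events.

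A second reply is that the stopping bullet sits in the Action row and follows from the Event row. An unrelated, unlisted AE never reaches it, and the bullet then matches criterion 5. This is the likely intent, and it stands as an interpretation. The wording does not say it, and the bullet beside it does carry the limit. Criterion 6 in Section 3.3.4.1 also allows stopping for AEs without requiring relatedness, so stopping for an unrelated event is not foreign to the protocol. That criterion, however, depends on the patient no longer being able to receive the drug, not on grade 2 alone.

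A reader might infer that the comparator is systematically under-dosed and PFS biased in favour of afatinib. The documents do not support that: they give no frequency of unrelated mucositis or of unrelated grade 2 events at 20 mg/m², and no link from such dose changes to PFS.

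**Conclusion.** The point holds as a conflict between two dosing rules and should be corrected. It is direct for mucositis, and for a listed laboratory value recorded as an unrelated AE. Its size per mucositis event is a permanent cut of 20%, 25% or 33% under the table against none under the sentence. For the stopping bullet the finding is narrower: its literal wording is over-broad and in tension with the skip-one-dose permission. A reader might infer that the bullet breaks the rule against reducing for an unrelated AE. It does not, because it orders no reduction.

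The conclusion assumes that an investigator can judge grade 2 mucositis unrelated, which Section 5.2.2.1.4 provides for. The primary analysis is not altered: it uses the randomised set, and SAP Section 6.2 plans no per-protocol set. What is affected is methotrexate dosing at the site, the C1 classification and the descriptive summaries of dose reductions. The rationale for Global Amendment 4 speaks of ongoing patients on afatinib, so few or no methotrexate patients may remain on treatment. The remaining value would then lie mainly in a settled standard for judging past dose changes.

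**What to change.** (a) In the sentence under Table 4.1.4.2: 2, limit its scope to *any unrelated AE other than the events listed in Table 4.1.4.2: 2*. This keeps the safety triggers independent of cause and both methotrexate tables consistent.

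(b) Reword the second stopping bullet to *any drug-related AE of CTCAE grade ≥ 2, or any other event listed above, at 20 mg/m² per week*. A listed event at the lowest dose then stops treatment, in line with criterion 5, and an unrelated, unlisted event does not.

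If the sponsor prefers to limit mucositis to drug-related cases, the line must change in both tables: in Table 4.1.4.2: 1 for continuing the current dose, and in Table 4.1.4.2: 2. The laboratory triggers would still need the exemption in (a) if they are meant to apply regardless of cause.

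The cost is one clause and one reworded bullet. Causality is already recorded in the CRF under Section 5.2.2.1.4, so no new data, visits, tests or patients are needed.

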4.1.5 Blinding and procedures for unblinding

4.1.5.1 Blinding

There will be no blinding as discussed in [Section 3.2](#). The eCRF will contain information on randomised treatment.

4.1.5.2 Procedures for emergency unblinding

Not applicable.

4.1.6 Packaging, labelling, and re-supply

For details of packaging and the description of the label, refer to the ISF.

Trial drug packages will have unique medication numbers, which will be used for tracking purposes only. The medication numbers are different from the randomization numbers.

Afatinib will be supplied as film-coated tablets. Available dosage strengths will be 50 mg, 40 mg, 30 mg, and 20 mg. Tablets will be supplied in child-resistant, tamper-evident bottles. Each bottle will contain 30 film-coated tablets of identical dosage strength.

Methotrexate will be supplied as vials containing 2 ml of 25 mg/ml solution.

Afatinib bottles and methotrexate vials will be labelled according to local regulations and will include the following as a minimum;

- Trial number (1200.161)
- Product name
- Contents of the bottle/vial
- Strength
- Batch number
- Medication number
- Use-by date
- Storage information
- Instructions for use
- Sponsor name and address
- A statement that the medication is for clinical trial use only.

4.1.7 Storage conditions

Trial medication, which will be provided by the sponsor, must be kept in a secure, access-controlled storage area under the storage conditions defined below until administered to patient. A temperature log must be maintained to make certain that the drug supplies are stored at the correct temperature. For facilities with a central alarm system, a print out of the temperature curves can be used and filed in the ISF.

Afatinib tablets may be stored according to the storage conditions defined on the medication label. Any temperature excursion has to be reported to BI. BI needs to decide whether the impacted Afatinib is usable or not and inform site the decision. Documentation of this event should be filed in the ISF. Tablets must be stored in the original package in order to protect from light. Film-coated tablets are humidity-sensitive; therefore, bottles must be kept tightly closed.

Methotrexate will be stored in accordance with the instruction on the label.

4.1.8 Drug accountability

The investigator or delegate (e.g. pharmacist or investigational drug storage manager) will receive the investigational drugs from the sponsor when the following requirements are fulfilled:

- approval of the trial protocol by the institutional review board (IRB) / ethics committee,
- availability of a signed and dated clinical trial contract by related parties
- approval/notification of the regulatory authority, e.g. competent authority,
- availability of the curriculum vitae of the principal investigator,
- availability of a signed and dated CTP or immediately imminent signing of the CTP,
- if applicable, availability of the proof of a medical licence for the principal investigator,

The investigator or delegate must maintain records of the product's delivery to the trial site, the inventory at the site, the use by each patient, and – upon check of the Clinical Research Associate (CRA) – the disposition of used and unused product(s) or alternative return to the sponsor. Upon completion of the trial, the investigator or delegate submits to BI a copy of the investigational drug dispensing and return log.

These records will include dates, quantities, batch/serial numbers, expiry ('use by') dates, and the unique code numbers assigned to the study medication and trial patients. The investigator or delegate will maintain records that document adequately that the patients were provided the doses specified in the CTP and reconcile all investigational products received from the sponsor. At the time of local destruction by site, return to the sponsor and/or appointed CRO, the investigator or delegate must verify that all unused or partially used drug supplies have been returned by the clinical trial patient and that no remaining supplies are in the investigator's possession.

4.2 CONCOMITANT THERAPY, RESTRICTIONS, AND RESCUE TREATMENT

All concomitant (non-oncological) therapies (except for those listed in [Section 4.2.2](#)) are allowed. No additional oncological concomitant therapies are allowed during the treatment period with Afatinib or methotrexate. The exception is palliative radiotherapy to bones (see [Section 4.2.1](#), Additional treatments).

All concomitant therapy, except for vitamins or appetite stimulants (with the exception of megestrol acetate; megestrol acetate is recorded in the eCRF), which are taken between the screening visit and 28 days after the last administration of Afatinib/methotrexate, should be recorded in the eCRF: Trade name, reason for use, and dates of administration must be documented.

For anti-cancer treatment (see [Section 5.3.2.2](#)), anti-emetic and anti-diarrhoeal also total daily dose and the respective unit must be documented.

If patients receive parenteral nutrition during the trial, the components do not need to be specified in detail. It is sufficient to report as "parenteral nutrition". If a patient requires anaesthesia, it will be sufficient to indicate "anaesthesia" without specifying the drug.

Concomitant therapy for treatment of an AE, which has to be documented after the end of active treatment (i.e. AE which persists after the end of active treatment or which is drug related), have to be documented as long as the AE is reported.

4.2.1 Rescue medication, emergency procedures, and additional treatments

- **Rescue medication**

Rescue medications to reverse the actions of Afatinib are not available. Side effects of these treatments should be treated symptomatically.

The current version of the IB lists the AEs expected with Afatinib. Suggested treatments for diarrhoea, mucositis/stomatitis and dermatological AEs are described in [Section 4.2.3](#).

Side effects of methotrexate should be treated symptomatically and according to SPC/PI and local practice. In case of over dosage with methotrexate, calcium folinate which can diminish the toxicity and counteract the effects of methotrexate should be administered according to recommendations in the SPC/PI or local practice.

- **Emergency procedures**

Careful assessment of all patients with an acute onset and/or unexplained worsening of pulmonary symptoms (dyspnoea, cough, fever) should be performed to exclude ILD (Afatinib) or non-specific pneumonitis (methotrexate). Study medication should be interrupted pending investigation of these symptoms. If ILD (Afatinib treated patients) or methotrexate induced lung disease is diagnosed, study medication should be permanently discontinued and appropriate treatment should be administrated as necessary.

For patients treated with Afatinib: Patients who present with symptoms of keratitis, such as acute or worsening eye inflammation, lacrimation, light sensitivity, blurred vision, eye pain and/or red eye should be referred promptly to an ophthalmic specialist. If a diagnosis of ulcerative keratitis is confirmed, treatment with Afatinib should be interrupted or discontinued. If keratitis is diagnosed, the benefits and risks of continuing treatment with Afatinib should be carefully considered. Afatinib should be used with caution in patients with a history of keratitis, ulcerative keratitis or severe dry eye. Contact lens use is a risk factor for keratitis and ulceration.

- **Additional treatments**

During trial participation symptomatic treatment of tumour associated symptoms is allowed. Concomitant medications or therapy to provide adequate care may be given as clinically necessary. In this trial, best supportive care (BSC) in both treatment arms will be defined as the best care available judged by the attending physicians, according to the institutional standards for each centre. BSC includes e.g. nutritional support, antibiotics, analgesics, oxygen, anti-emetics, transfusions, or any other symptomatic therapy (with the exception of cytotoxic chemotherapy) and/or assistance of a psychotherapist and/or physiotherapist. Localised radiation therapy to bones to alleviate pain is allowed provided that the total dose delivered is in a palliative range according to institutional standards and does not involve a target lesion(s) for

response evaluation. Study medication should be delayed during palliative radiotherapy and may be resumed once the patient has recovered from any radiation associated toxicity.

4.2.2 Restrictions

4.2.2.1 Restrictions regarding concomitant treatment

Additional experimental treatment is not allowed concomitantly with the administration of study medication, nor any additional anti-cancer therapy between four weeks prior to randomization and until EOT (with the exception of megestrol acetate and palliative short-course radiotherapy to bone lesions for pain relief).

Afatinib is a substrate of the P-glycoprotein (P-gp) transporter. Caution should be exercised when combining Afatinib with P-gp modulators ([U03-3218](#)). For a list of potent P-gp inhibitors and inducers (see [Appendix 10.5](#)). Patients treated with methotrexate should not receive any of the prohibited medications as listed in the current SPC/PI for methotrexate therapy.

